2.7.1. Documentation folder

Each doctor will be provided with a documentation folder containing a complete set of documents for 7-8 patients + 2 extra sets in case of lost or damage of study documents including:

- One protocol of the observation plan;
- Documents for 7-8 patients (*Patient Informed Consent Form, Case report form (CRF) with 7-8 Adverse event/adverse drug reaction/special situation reporting forms*).
- 2 extra sets in case of lost or damage of study documents (*Patient Informed Consent Form, CRF; Adverse event/adverse drug reaction/special situation reporting forms*)

2.7.2 Study schedule

According to the design of multicentre, non-intervention, open-label, incomparative, ambispective study in patients with HTN and CAD treated with a bisoprolol/perindopril SPC, three visits will be enough to include patients, evaluate the treatment effectiveness and safety, as well as to adjust the dose of the study drug* (3,8).

The following visits are scheduled:

1. Screening period: will be retrospectively performed to ensure each patient fulfills inclusion/non-inclusion criteria
2. Inclusion visit (V0): month 0;
3. Follow-up visit (V1): at 1 month after the V0 visit;
4. Final visit (V2): at month 3 after the visit V0 or in case of perindopril/ bisoprolol SPC treatment withdrawal.

* *In renal impairment, it is necessary to adjust the dose depending on the degree of impaired renal function (creatinine clearance)*

2.7.3. Methods and measurements of clinical parameters

Measurement of the clinical BP by Korotkov's method in the sitting position in the doctor's office at the regular visit. BP will be measured on the same arm of the patient after 5 minutes of the rest. BP and HR will be measured thrice with an interval of 1-2 min; the average value of the last two measurements will be considered as the BP value measured at the visit; if the differences between two consecutive measurements of SBP are ≥ 15 mm Hg, it is necessary to perform the repeated BP measurement.

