- To describe a proportion of patients who achieved resting HR less than 60 bpm at week 12 of prospective observation.
- To estimate association between the resting HR and achievement of target level of BP at week 12 of prospective observation.
- To describe adherence to the treatment with bisoprolol / perindopril in hypertensive patients with previous MI during the prospective observational period of 12 weeks.
- To describe the tolerability of treatment with bisoprolol / perindopril in hypertensive patients with previous MI during 12 week prospective observation.

Outcome measures

Primary outcome measure:

- Change in the mean systolic and diastolic BP levels at week 12 of prospective observation compared to baseline among patients included in the study.

Secondary outcome measures:

- Change in mean systolic and diastolic BP levels at week 4 of prospective observation compared with baseline.
- Change in number of angina attacks per week at week 4 of prospective observation compared with baseline.
- Change in number of angina attacks per week at week 12 of prospective observation compared with baseline.
- Proportion of patients who were taking lipid lowering therapy (LLT) at week 12 of prospective observation.
- Proportion of patients receiving LLT who achieved target levels of LDL C at week 12 of prospective observation.
- Proportion of patients who achieved SBP \leq 140 mm Hg and DBP \leq 90 mm Hg at week 4 of prospective observation.
- Proportion of patients who achieved SBP \leq 140 mm Hg and DBP \leq 90 mm Hg at week 12 of prospective observation.
- Proportion of patients younger than 65 who achieved SBP \leq 130 mm Hg and DBP \leq 80 mm Hg at week 4 of prospective observation .
- Proportion of patients younger than 65 who achieved SBP \leq 130 mm Hg and DBP \leq 80 mm Hg at week 12 of prospective observation.
- Proportion of patients older than 65 years who achieved SBP \leq 140 mm Hg and DBP \leq 90 mm Hg at week 4 of prospective observation.

- Proportion of patients older than 65 years who achieved SBP≤140 mm Hg and DBP ≤90 mm Hg at week 12 of prospective observation .
- Changes in the mean heart rate (HR) at week 4 of prospective observation compared with baseline.
- Changes in the mean heart rate (HR) at week 12 of prospective observation compared with baseline.
- Proportion of patients who achieved target level of resting HR (55-60 bpm) at week 4 of prospective observation.

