- Proportion of patients who achieved target level of resting HR (55-60 bpm) at week 12 of prospective observation.
- Correlation between the resting HR values stratified by groups and achievement of BP targets at week 12 of prospective observation .
- Proportions of patients with high, medium or low adherence to the treatment with SPC of bisoprolol/perindopril, assessed by MMAS-8 self-reporting questionnaire at week 4 of prospective observation.
- Proportions of patients with high, medium or low adherence to the treatment with SPC of bisoprolol/perindopril, assessed by MMAS-8 self-reporting questionnaire at week 12 of prospective observation.
- Incidence rate of adverse events/ adverse drug reactions and special situations during 12 week observational period of the study.

2 Methods and documentation

Study design and definitions

This is a multi-centre, observational, incomparative, ambispective study, which will retrospectively and prospectively collect clinical and socio-demographic data from medical records of patients with HTN and previous MI initiated with bisoprolol/perindopril SPC in real clinical settings.

Baseline data will be collected retrospectively from medical records of patients with HTN and a history of MI. Baseline data are defined as clinical parameters of interest available in medical records at the nearest date before or at the date of the initiation of SPC with Bisoprolol/ Perindopril.

To be included in the study for further prospective observation a patient should have been administered bisoprolol/ perindopril SPC within first three months before the Index Date. (*Fig.1*).

The Index date is a date when a decision to include a patient in the study for further 12 week prospective observation made by a treating physician after evaluation of recorded data to confirm patient's eligibility for the study.

Therefore, criteria for non-inclusion or inclusion of patients in the study are to be retrospectively evaluated by the treating physician using recorded clinical data available from medical records. Once a treating physician makes decision to include a patient in the study and, in particular, on the prospective observation for 3 months, a visit 0 (inclusion visit) to the clinic for obtaining signed patient's consent to participate in the study should be appointed and made within 1 month from the Index Date.

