4. Bisoprolol/perindopril SPC prescription 1-3 months before screening
5. Bisoprolol/perindopril SPC prescription in accordance with Russian SmPC, based on necessity in treatment with bisoprolol/perindopril SPC and separated from the decision to include the patient in the study
6. Clinical parameters of interest (Resting HR; SBP and DBP; frequency of angina attacks per week) are available in medical records for the nearest date before or at the date of the initiation of SPC with Bisoprolol/ Perindopril.

Non-inclusion criteria

1. Hypersensitivity to bisoprolol, perindopril, excipients of the medicine, or other ACE inhibitors.
2. Any contraindication for bisoprolol/perindopril's SPC according to the instruction for medical use
3. CAD, angina pectoris of functional class IV according to the CCS classification (Appendix 1).
4. Chronic heart failure of class III-IV according to the New York Heart Association (NYHA) functional classification of heart failure (Appendix 3).
5. Cerebrovascular diseases (ischemic, haemorrhagic stroke, or transient ischemic attack) within the past 6 months prior to inclusion in the study.
6. A history of revascularization procedure within 3 months prior to inclusion in the study.
7. Hypertrophic obstructive cardiomyopathy.
8. Office BP \geq 180/110 mm Hg on treatment
9. Type 1 diabetes mellitus and decompensated type 2 diabetes mellitus.
10. Bradycardia with a heart rate of less than 60 beats per minute.
11. Atrioventricular block (II-III degree), sinoatrial block, or sick sinus syndrome.
12. Severe bronchial asthma or severe chronic obstructive pulmonary disease.
13. Arterial hypotension (BP less than 100/70 mm Hg).
14. Pregnancy, breastfeeding.
15. Secondary hypertension.
16. Severe decompensated diseases of organs and systems requiring continuous treatment.
17. Current participation in another clinical trial and within 30 days prior to signing informed consent.

Treatment during the study

Treatment with the studied drug

bisoprolol 5 mg + perindopril 5 mg once daily
bisoprolol 5 mg + perindopril 10 mg once daily
bisoprolol 10 mg + perindopril 5 mg once daily
bisoprolol 10 mg + perindopril 10 mg once daily

A minimum dosage may also be prescribed:

bisoprolol 2.5 mg + perindopril 2.5 mg 1 time per day (1/2 tablet of bisoprolol 5 mg + perindopril 5 mg)

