2.7.4 Study procedures and data collection

The plan at each visit during the study is presented in Table 1.

Patients will be provided with the self-observation diaries where they will record the BP values self-measured at home, the number of anginal attacks and the need to use short-acting nitrates.

Table 1 – Plan of visits during the study

Procedures	Screening period (retrospective)	V0 Inclusion visit (month 0)	V1 Follow-up visit (month 1)	V2 Final visit (month 3)
Obtaining patient informed consent		×		
Inclusion/ non-inclusion criteria	×	×		
Demographic data		×		
Risk factors and lifestyle		×		
Medical history		×		
Medical records on Resting HR; SBP and DBP; frequency of angina attacks per week for the nearest date before or at the date of the initiation of SPC with Bisoprolol/ Perindopril		×		
Physical examination and vital signs (rest heart rate and BP) at the office visit		×	×	×
Current symptoms and the use of short-acting nitrates		×	×	×
Number of angina attacks per week		×	×	×
Current use of antianginal agents		×	×	×
Current use of other cardiovascular drugs		×	×	×
Current use of other drugs		×	×	×
Treatment adherence assessed by the patient (Morisky Medication Adherence Scale)		×	×	×
Current use of bisoprolol/perindopril SPC and reasons for discontinuation/ disruption of the treatment (if applicable)		×	×	×
Bisoprolol/perindopril SPC dose adjustment and reasons Bisoprolol/perindopril SPC dose adjustment		×	×	×
Adverse events/drug reactions/special situations		×	×	×

COLLECTION DATA:

2.7.4.1. Data evaluation during the screening period:

HCPs participating in the study will conduct a retrospective analysis of patient's records for the purpose of evaluating patient's eligibility to be enrolled in the study. Patients with HTN and a

history of MI, who had been initiated with bisoprolol/perindopril SPC within first three months before the Index Date (see a definition in Study Design and definitions of Section 2) and who meet other inclusion / non inclusion criteria will be included in the study if they sign a consent form at the inclusion visit.

2.7.4.1. Data collection at the inclusion visit (V0):

- Obtaining patient informed consent;
- Checking for inclusion/non-inclusion criteria;
- Physical examination and vital signs;
- Current status of taking bisoprolol/perindopril SPC and a dose regimen;
- Number of weekly angina attacks;
- Current symptoms and the use of short-acting nitrates;
- Current use of antianginal agents;

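### Baseline BP comes from the chart with no limit on its age or condition on its method, while week-12 BP follows a fixed procedure, so part of the primary change may be measurement that the plan cannot separate from treatment

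*Combined protocol and SAP*

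**What the plan says.** The primary outcome (section 1, Outcome measures) is: "Change in the mean systolic and diastolic BP levels at week 12 of prospective observation compared to baseline among patients included in the study". The study has one group and no comparator.

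**Baseline.** Section 2, Study design and definitions, states: "Baseline data will be collected retrospectively from medical records of patients with HTN and a history of MI". It defines these data as "clinical parameters of interest available in medical records at the nearest date before or at the date of the initiation of SPC". Inclusion criterion 6 asks only that the values exist: "Clinical parameters of interest (Resting HR; SBP and DBP; frequency of angina attacks per week) are available in medical records for the nearest date". Table 1 in section 2.7.4 lists the chart values for collection at V0, without mentioning their date or how they were obtained.

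**Study visits.** Section 2.7.3 sets a procedure for seated office BP by Korotkov's method. On arm and rest it says: "BP will be measured on the same arm of the patient after 5 minutes of the rest". Three readings then follow, 1-2 minutes apart. The rule for the value used is that "the average value of the last two measurements will be considered as the BP value measured at the visit". A repeat is required when consecutive systolic readings differ by 15 mm Hg or more. Table 1 schedules "Physical examination and vital signs (rest heart rate and BP) at the office visit" at V0, V1 and V2.

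**Analysis.** Section 4, Statistical analysis, plans descriptive statistics and two-sided tests at 0.05. It contains no sensitivity analysis for the method or the age of the baseline reading.

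**The concern.** A before-after change in one group can be read as a response to treatment only if both ends are measured alike. Here one end has a full set of rules and the other has only a selection rule, the nearest date. A systematic difference between the two would pass in full into the mean change. No control group would cancel it, and a larger sample would only estimate the biased value more precisely.

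There are two routes. The first is method: rest and the dropping of the first reading are required at study visits but not for the chart value. The second is time: the nearest chart value may be recent or old, and an old one may not describe BP when the SPC was started.

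At stake is how the main effectiveness figure is read. The sample-size section presents 6.3 mm Hg as detectable, and a shift of a few mm Hg is not small beside that.

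**Working it through.** **1. The two ends side by side**

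| Feature | Baseline (chart) | V0, V1, V2 |
|---|---|---|
| Timing | Nearest date before or at SPC start; no look-back limit | Scheduled visit |
| Rest | Not specified | 5 minutes |
| Position, arm | Not specified | Seated, same arm |
| Number of readings | Not specified | Three, 1-2 minutes apart |
| Value used | Whatever was recorded | Mean of the last two |

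Section 2.7.3 is written for measurements still to be made, so it cannot govern a reading charted before the study. V0 does follow the procedure, but inclusion criterion 4 puts the SPC prescription 1-3 months before screening. V0 is therefore an on-treatment value and cannot replace the baseline.

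**2. The plan's own figure**

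Inputs from Calculation of the sample size: n = 500, SD 50 mm Hg, power 80%, significance level 0.05. Two-sidedness is from section 4.

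Detectable change = SD × (z for 0.975 + z for 0.80) / √n = 50 × 2.8016 / √500 = 6.26 mm Hg, which rounds to the stated 6.3.

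The figure reproduces and is not in dispute. It treats the baseline SD of 50 as the SD of the change. With equal SDs at both times, that holds at a correlation of 0.5, since 50 × √(2 × (1 − 0.5)) = 50. It allows for random error only.

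**3. What a systematic shift would do**

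The documents give no size for a shift and no SD of change. The shifts below, and the SD of 20, are assumptions.

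- SE at SD 50: 50/√500 = 2.24 mm Hg. A 3 mm Hg shift is 3/2.24 = 1.3 SEs.
- SE at SD 20: 20/√500 = 0.89 mm Hg. A 3 mm Hg shift is 3/0.89 = 3.4 SEs.

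With no true change in BP, the chance of a statistically significant fall from the shift alone is Φ(shift/SE − 1.96):

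| Assumed downward shift, mm Hg | Chance at SD 50 | Chance at SD 20 |
|---|---|---|
| 1 | 6.5% | 20% |
| 2 | 14% | 61% |
| 3 | 27% | 92% |
| 5 | 61% | >99% |
| 8 | 95% | >99% |

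With no shift, the chance in this direction is 2.5%.

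Against the plan's 6.3 mm Hg, a shift of 2 mm Hg is 2/6.3 = 32% and one of 5 mm Hg is 5/6.3 = 79%. Against an assumed observed fall of 20 mm Hg, the same shifts are 10% and 25%. A shift in the other direction would hide a real fall by the same amount.

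**The case against.** The strongest reply is that nothing shows a shift exists. Section 2.7.3 describes ordinary seated office measurement at a regular visit, and some or all chart readings may have been taken in the same way. The retrospective baseline is also deliberate: section 2 explains that screening from records guards against prescribing driven by the study. The plan calls itself exploratory and descriptive, so the matter could be treated as a limitation to mention in the report.

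Much of this stands. A chart baseline follows from observing patients already on treatment, and the fix keeps it. Three stronger readings are tempting, and the documents support none of them:

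- **That part of the fall definitely comes from the change of method.** How the chart readings were taken is not stated, so this is only possible.
- **That the bias must exaggerate the fall.** A downward shift is plausible, because rest and the dropping of the first reading are required only at study visits. The documents give no direction, and an old baseline could err either way.
- **That heart rate is affected in the same way.** HR is also read three times, but the averaging rule is stated for BP only.

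The descriptive label does not remove the point. A shift biases a descriptive mean as much as a tested one, and the plan does foresee tests and a detectable difference.

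**Conclusion.** The asymmetry is in the documents, and no planned analysis would reveal its effect. The supportable conclusion is that part of the week-12 BP change may reflect measurement differences or an outdated baseline, and that this single-group plan cannot separate that part from a treatment effect.

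The size is unknown. The 3 mm Hg example and the SD of 20 are assumptions, and the number of SEs depends heavily on which SD applies. A reader might infer that a 3 mm Hg shift always exceeds three SEs, but at the plan's own SD it is 1.3. What does not depend on either assumption is that any such shift enters the mean change in full and does not diminish with n.

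This does not invalidate the primary analysis. The plan should be changed on this point, because without the date and method of the chart reading the question cannot be answered after database lock.

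**What to change.** 1. In the CRF, record the date of the chart BP and, where known, how it was taken: number of readings, rest and averaging. The CRF is not among the documents, so some of these fields may already exist.
2. Record all three BP readings at V0, V1 and V2.
3. Keep the stated primary analysis. Pre-specify a sensitivity analysis that repeats it in patients whose baseline was taken within a fixed look-back before SPC start (for example 30 days) and, where known, by a comparable method.
4. Report an analysis of the first reading at V1 and V2 only as a partial check of the discard rule. That reading still follows 5 minutes' rest, so it does not match a chart value of unknown method.
5. Report the V0-to-V2 change as supportive only. Both ends are measured alike, but patients are already on the SPC at V0, so it does not estimate the change from before treatment.
6. State the limitation in the report.

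The cost is a few CRF fields, mostly for readings already taken, and one or two extra tables. The restricted analysis loses patients and so precision. If half of 500 qualified (an assumption), the SE at SD 50 would rise from 2.24 to 50/√250 = 3.16 mm Hg. Chart method will often be unknown, so the look-back restriction may be the more usable part.

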2.7.4 Study procedures and data collection

The plan at each visit during the study is presented in Table 1.

Patients will be provided with the self-observation diaries where they will record the BP values self-measured at home, the number of anginal attacks and the need to use short-acting nitrates.

Table 1 – Plan of visits during the study

Procedures	Screening period (retrospective)	V0 Inclusion visit (month 0)	V1 Follow-up visit (month 1)	V2 Final visit (month 3)
Obtaining patient informed consent		×		
Inclusion/ non-inclusion criteria	×	×		
Demographic data		×		
Risk factors and lifestyle		×		
Medical history		×		
Medical records on Resting HR; SBP and DBP; frequency of angina attacks per week for the nearest date before or at the date of the initiation of SPC with Bisoprolol/ Perindopril		×		
Physical examination and vital signs (rest heart rate and BP) at the office visit		×	×	×
Current symptoms and the use of short-acting nitrates		×	×	×
Number of angina attacks per week		×	×	×
Current use of antianginal agents		×	×	×
Current use of other cardiovascular drugs		×	×	×
Current use of other drugs		×	×	×
Treatment adherence assessed by the patient (Morisky Medication Adherence Scale)		×	×	×
Current use of bisoprolol/perindopril SPC and reasons for discontinuation/ disruption of the treatment (if applicable)		×	×	×
Bisoprolol/perindopril SPC dose adjustment and reasons Bisoprolol/perindopril SPC dose adjustment		×	×	×
Adverse events/drug reactions/special situations		×	×	×

COLLECTION DATA:

2.7.4.1. Data evaluation during the screening period:

HCPs participating in the study will conduct a retrospective analysis of patient's records for the purpose of evaluating patient's eligibility to be enrolled in the study. Patients with HTN and a

history of MI, who had been initiated with bisoprolol/perindopril SPC within first three months before the Index Date (see a definition in Study Design and definitions of Section 2) and who meet other inclusion / non inclusion criteria will be included in the study if they sign a consent form at the inclusion visit.

2.7.4.1. Data collection at the inclusion visit (V0):

- Obtaining patient informed consent;
- Checking for inclusion/non-inclusion criteria;
- Physical examination and vital signs;
- Current status of taking bisoprolol/perindopril SPC and a dose regimen;
- Number of weekly angina attacks;
- Current symptoms and the use of short-acting nitrates;
- Current use of antianginal agents;
- Current use of other cardiovascular drugs with doses for calcium channel blockers, diuretics, nitrates and statins;
- Baseline assessment of adherence to bisoprolol/perindopril SPC done by patient-reported 8 item Morisky Medication Adherence Scale;
- Adverse events/drug reactions/special situations.

2.7.4.2. Data collection at the follow-up visit (V1):

- Physical examination and vital signs;
- Current status of taking bisoprolol/perindopril SPC and a dose regimen;
- Number of weekly angina attacks;
- Current symptoms and the use of short-acting nitrates;
- Current use of antianginal agents;
- Adherence to bisoprolol/perindopril SPC assessed by patient-reported 8 items Morisky Medication Adherence Scale;
- Current use of other cardiovascular drugs with doses for calcium channel blockers, diuretics, nitrates and statins;
- Adverse events/drug reactions/special situations;

2.7.4.3. Data collection at the final visit (V2):

- Physical examination and vital signs;
- Current status of taking bisoprolol+perindopril SPC and a dose regimen;
- Number of weekly angina attacks ;
- Current symptoms and the use of short-acting nitrates;
- Current use of antianginal agents;
- Current use of other cardiovascular drugs with doses for calcium channel blockers, diuretics, nitrates and statins;

- Adherence to bisoprolol/perindopril SPC assessed by patient-reported 8 items Morisky Medication Adherence Scale;
- Adverse events/drug reactions/special situations;

[figure not shown]

Figure 1. The scheme of the PRIDE study.

